7 STUDY DESIGN

7.1 Overview

This study consists of a programme of work that is centred around a UK-based, multi-centre cohort study of women who are pregnant or have recently been pregnant.

The overall research question is: "Can an electronically-embedded, enhanced Maternal Early Warning Score (eMOEWS) with behaviourally-informed escalation pathways prevent maternal 'near-miss', 'severe morbidity' events and mortality?"

The overall research aim is to prevent maternal morbidity and mortality and reduce inequalities in outcomes by developing, refining, validating, embedding, and testing an eMOEWS with clinical escalation pathways.

The initial programme of work, covered by this protocol, is divided into four workstreams as below. The work described in this protocol is intended (subject to funder agreement) to be immediately followed by a prospective study to assess the clinical and health economic effects of implementation of the eMOEWS and the associated escalation pathway (for which a separate protocol will be written and separate approvals sought).

7.2 Workstream 1

Workstream 1 will develop ‘near-miss’ and ‘pre-near-miss’ (indicating deviation from normal pregnancy such that intervention is required to avoid progression to a ‘near-miss’ event) definitions electronically derivable from routine data by a literature review, followed by an international Delphi process. The identification performance of these definitions will be assessed using data from MBRRACE-UK and three NHS hospitals. See Figure 1 for an overview of the workstream 1 workflow.

We will convene an expert clinical panel to define the pathological pathways to “near-miss” as defined by the World Health Organisation near-miss events and other published criteria. We will include multi-professional expertise (e.g., midwifery, obstetrics, anaesthetics, obstetric medicine, pathology, clinical epidemiology, critical care). We will use these pathways to identify candidate specific pre-near-miss maternal complications that could lead to “near-miss” events (or death).

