We will identify consensus definitions of “pre-near-miss” criteria where possible from existing core outcome sets (such as the HDR UK Phenotype library and others (45,46)), along with methods to identify these outcomes from routinely collected data. Where there is any uncertainty regarding the definition of “pre-near-miss” criteria, we will conduct targeted literature reviews. Where consensus definitions are not available, they will be determined by the expert panel.

We will map definitions to the Maternity Services Dataset (MSDS), Hospital Episode Statistics and routinely available electronic patient record data in our partner hospitals, identifying where and what routine data augmentation may be required for specific definitions and where surrogates are available.

Definitions (consensus or expert panel), methods for their identification and any required routine data augmentation or surrogate available data fields will inform a three-round international consensus Delphi process, including the patient voice. The Delphi process will follow guidance from the Core Outcome Measures in Effectiveness Trials (COMET) Initiative (47). In round 1, participants will also be asked to identify missing important definitions. A Delphi facilitator will curate Round 1 results. Delphi participants will be asked to rate definitions on a 9-point Likert scale from 1 (not important) to 9 (critically important) in round 2. Following further curation, the results from Round 2 (all definitions, along with summary statistics of their respective scores (mean, median, range) will be fed back to the Delphi panel, allowing each member to see how the panel had voted on each definition. Using this information, each member will be asked to re-score each definition using the same 9-point scale as used in Round 2. Definitions rated 7-9 by 70% or more of the panel or 1-3 by less than 15% in at least one stakeholder group will be included in the final list (47).

The final list will again be assessed by our expert panel and mapped against routine data reviewed to achieve 'near-miss' and 'pre-near-miss' for identification performance testing.

We will use retrospective data from three representative collaborator NHS hospitals (who will form part of the retrospective cohort) and from MBRRACE-UK, reviewing deaths, near-miss and pre-near-miss cases to estimate identification performance using the new definitions.

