7.3.2 Workstream 2a

We will curate retrospective datasets from routine NHS maternity unit electronic data to encompass the work in section 2b and 3b. Data will encompass variables required for prediction and data required for maternal and neonatal outcomes (to allow assessment of the predictive ability of the scores for adverse neonatal outcomes). For data types see section 12.1.2.

The output of this workstream will be the external validation performance of existing MOEWS. Details of the methods that will be used to carry this out are reported in Section 11.2.2.

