7.3.3.3 Outcome measures

The primary outcome for MOEWS assessment for both data sources (WP2a&b) will be a combination of maternal death, 'near-miss' and 'pre-near-miss' events (as defined in WS1). Secondary outcomes will be maternal death, 'near-miss' and 'pre-near-miss' events, individually. For more details on the analysis methods see Section 11.2.3.

7.4 Workstream 3

Workstream 3 will develop an eMOEWS candidate variable list by literature review informing a further Delphi process. An optimal vital-signs MOEWS and a multivariable eMOEWS will be developed and validated, exploring regression models and machine learning (ML) approaches.

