7.4.1.2 Review strategy

We will undertake quality assessment of included studies, where possible using the QUIPS tool for prognostic factors, recommended by the Cochrane Handbook for the appraisal of studies of risk factors (53,54). The piloted data extraction form will follow the prognostic factors adaptation (CHARMS-PF) of the Critical Appraisal and Data Extraction for Systematic Reviews of Prediction Modelling Studies

(CHARMS) guidance (52). We will further synthesise available data using a semi-quantitative method previously described by Zaal et al. (55) and adapted by Dettmer et al (56).

7.4.1.3 *Delphi strategy*

We will assess the variables identified during our systematic review against those recorded in our partner maternity sites to inform availability for inclusion. We will use this information to inform a 3-round international Delphi process to compile a list of existing, electronically available variables which affect the risk of 'near-miss' and 'pre-near-miss' events (as defined in WS1). This will generate a candidate variable list. Our strategy will follow a similar process to that in WS1.

The Delphi participants will again be identified from author lists of articles included in our review of the literature to ensure diverse expertise and selection objectivity. We will also involve our PPI colleagues. In round one, variables identified from our literature review will be presented to the Delphi participants along with their purported effect on risk (protective vs predisposing). To provide structure, variables will be grouped into a small number of domains including but not limited to demographics, vital signs, and laboratory variables. Participants will again be asked to identify any variables felt to be important but not included, and whether these are felt to represent protective factors or predisposing factors. Round 1 results will then be collected and curated by a Delphi facilitator.

Subsequent rounds will follow the processes described in WS1.

The final candidate variable list will then be assessed against availability in the 8-12 sites followed by data extraction of available candidate variables as part of WS2a. For likely variable types see section 12.1.2.

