11.2.4 Workstream 3b

11.2.4.1 Model development

We will explore both regression and machine learning (ML) approaches for model development. We anticipate at least 5800 ‘near-miss’ or ‘severe morbidity’ events, with higher rates using our new definitions.

For approaches using regression models (e.g., logistic or Cox regression if censoring is an issue) we will assess pre-defined pairwise interactions and include non-linear relationships for continuous predictors (e.g., using fractional polynomials or restricted cubic splines) (66). Pairwise interactions may be used to address apparent discrepancies in model performance for specific subgroups, identified in WS2. We will investigate whether accounting for trends of repeated measurements within individuals (e.g., blood pressure) can be incorporated to improve predictive accuracy. We will additionally explore how performance varies when using a composite outcome versus developing different models for individual outcomes (e.g., sepsis, pre-eclampsia). This may be informed by the results from WS2. Where appropriate, we will consider using a least angle selection and shrinkage operator (LASSO) penalty (67).

In parallel we will investigate and compare ML approaches to developing a prediction model, including methods such as random forests, deep neural networks, Bayesian Gaussian processes and gradient-boosted decision tree survival models (37,68). Such models allow consideration of interactions between available variables providing “latent variables” (complex, non-linear transformations of the original input variables) that may improve prediction performance over the non-transformed input variables. We will prioritise principled, probabilistic methods that permit the incorporation of prior clinical knowledge, such that results are “interpretable”, avoiding the “black box” nature of much ML-oriented research in this area (68,69).

MOEWS are typically calculated several times during a woman’s pregnancy, and other candidate variables will also be measured repeatedly (for example, blood tests). The best way of accounting for these repeated measures in model development (and validation) is not well defined. Therefore, we will explore different options for how best to incorporate this.

Where applicable learning from the regression and machine learning approaches will be combined to achieve a final deliverable model.

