12.1.2 Workstream 2/3b

Electronic patient record data for datasets in workstream 2 and 3 will include both inpatient and outpatient data, with sources including:

- Patient administrative records (e.g., admission times, medical/surgical speciality, age, gender, ethnicity, ward locations/transfers)
- Diagnostic (ICD-10) and procedure coding (OPCS4)
- Vital signs/early warning score recording systems (e.g., blood pressure, heart rate, early warning score)
- Intensive care patient record systems
- Laboratory management systems (e.g., haematology, biochemistry, pathology, and microbiology)
- Electronic prescriptions/administrations
- Point of care testing (e.g., blood gas analysis)
- Electrocardiogram systems
- Echo cardiogram systems
- Diagnostic imaging data reports
- Peripartum monitoring (e.g. Cardiotocography)
- Maternal records from maternity electronic record systems (including the digital “red book”) and local maternity data sets submitted to NHS England (e.g., Maternity Services Data Set), including information on current and previous pregnancies and maternal (e.g., weight/height/BMI, smoking status) and neonatal outcomes/characteristics (e.g., APGAR, requirement for additional care)

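### Outcome criteria may be defined by the same vital-sign or laboratory fields that feed the scores, and no planned analysis separates such events, so performance and score rankings can be inflated

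*Protocol*

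**What the plan says.** **How outcomes are chosen.** Protocol section 7.2 develops "definitions electronically derivable from routine data by a literature review, followed by an international Delphi process". Selection is by panel rating of importance. Definitions are mapped to national datasets and to "routinely available electronic patient record data in our partner hospitals, identifying where and what routine data augmentation may be required", with surrogate fields allowed. Pre-near-miss is described as a departure from normal pregnancy that calls for intervention.

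**How outcomes are pooled.** Section 7.3.3.3: "The primary outcome for MOEWS assessment for both data sources (WP2a&b) will be a combination of maternal death", near-miss and pre-near-miss events. The secondary outcomes are those three components taken one at a time.

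**Where predictors come from.** Section 7.3.2, on the same extract: "Data will encompass variables required for prediction and data required for maternal and neonatal outcomes". Section 7.4.1.3 groups candidate predictors in domains "including but not limited to demographics, vital signs, and laboratory variables". Section 11.2.4.1 adds that "other candidate variables will also be measured repeatedly (for example, blood tests"). Section 5.1 lists heart rate, blood pressure, oxygen saturation, respiratory rate and conscious level as the inputs of current MOEWS.

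**Shared sources.** Section 12.1.2 lists "Vital signs/early warning score recording systems (e.g., blood pressure, heart rate, early warning score") and laboratory systems, alongside diagnostic and procedure codes, intensive care, prescribing and maternity records. No source is assigned to the predictor or the outcome side.

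**Timing.** Sections 11.2.2, 11.2.3 and 11.2.4.3 plan to report how far ahead of events the scores alert.

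**The concern.** If a criterion is a threshold on a variable that a score also uses, the reading that defines the event can be the reading that triggers the alert. For such events the score restates the outcome, and its c-statistic and sensitivity rise without any gain in warning.

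The comparison between scores is the more exposed part. A secondary objective in section 6 compares the eMOEWS with the new vital-signs MOEWS, the best published MOEWS and the national tool. Section 5.2 gives, among its reasons for expecting a multivariable score to do better, that WHO near-miss events need measures other than vital signs for their definition. A score holding laboratory values could therefore gain on laboratory-defined events partly because it contains the defining field.

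Overlap is most plausible for pre-near-miss, which moves the outcome towards early deterioration. Section 11.3.1 expects pre-near-miss to be more frequent than the severe rates used for sample size, so this tier may dominate the composite.

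**Working it through.** **1. The plan's own figures.** Inputs are from sections 11.3.1 and 11.3.2.
- Retrospective cohort: 5,875 births × 12 sites × 50/12 years = 293,750 (stated 293,200).
- Prospective cohort: 5,875 × 12 × 28/12 = 164,500 (stated 164,300).
- Events at 2%: 0.02 × 293,200 = 5,864 and 0.02 × 164,300 = 3,286.

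The figures reproduce closely. None of them settles the overlap question; they serve only to scale it.

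**2. Effect on the c-statistic.** The c-statistic is the chance that a random case scores higher than a random non-case. With one pool of non-cases it is a case-weighted average:

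measured c = (1 − f) × c0 + f × c_ov

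Here f is the share of events defined by a score input, c0 is the c-statistic on the other events and c_ov the c-statistic on the overlapping ones. The protocol gives neither f nor c_ov, so both are assumed. For c0, 0.80 is used, the value assumed in section 11.3.2.

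| f | c_ov = 0.90 | c_ov = 1.00 |
|---|---|---|
| 0% | 0.800 | 0.80 |
| 5% | 0.805 | 0.81 |
| 10% | 0.810 | 0.82 |
| 25% | 0.825 | 0.85 |
| 50% | 0.850 | 0.90 |

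With c0 = 0.75 and c_ov = 0.98, the result is 0.773, 0.796 and 0.842 at f = 10%, 20% and 40%.

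**3. Effect on sensitivity.** If every overlapping event alerts at the event itself, measured sensitivity = (1 − f) × s0 + f. An assumed s0 of 0.60 becomes 0.62, 0.64, 0.70 and 0.80 at f = 5%, 10%, 25% and 50%.

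**4. Effect on a comparison.** Take two scores with c = 0.80 on independently defined events. Let 10% of events be laboratory-defined, let one score hold that field (c_ov = 1.00), and let the other stay at 0.80 on those events. The measured values are 0.82 and 0.80, a gap of 0.02 due to overlap alone.

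**5. Against sampling error.** The Hanley–McNeil standard error at c = 0.80 uses 3,286 events and 164,300 − 3,286 = 161,014 non-events, one observation per woman. Q1 = 0.8/1.2 = 0.6667 and Q2 = 2 × 0.64/1.8 = 0.7111.

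SE² = [0.16 + 3,285 × (0.6667 − 0.64) + 161,013 × (0.7111 − 0.64)] / (3,286 × 161,014), so SE ≈ 0.0047.

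A shift of 0.02 is 0.02/0.0047 ≈ 4 standard errors. A large sample narrows the interval around a shifted value and does not remove the shift.

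**6. What the planned safeguards reach.**
- Lead time (11.2.2 to 11.2.4.3) shows alerts at or near time zero, but leaves those events in the c-statistic, sensitivity, calibration and decision curves.
- Severity-tier outcomes (7.3.3.3) remove pre-near-miss from one analysis, but do not isolate a laboratory-defined near-miss.
- Internal-external and later-period validation (11.2.4.3) use the collaborating sites, so any overlap is reproduced.
- Record review (7.2.1) checks whether codes identify conditions, not whether criteria are independent of score inputs.

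**The case against.** A reader might infer that the outcomes are in fact built from vital signs and laboratory values, that performance is therefore inflated, and that the protocol does nothing about it. The documents do not support that reading.

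- The criteria do not yet exist. Section 7.2 draws on core outcome sets and a phenotype library, sections 7.2.1 and 8.1.1.2 speak of coded criteria, and section 12.1.2 offers codes, intensive care and prescribing data as well. Many criteria may share no field with any score.
- The remark in section 5.2 about WHO near-miss also suggests limited overlap for vital-signs-only scores.
- Lead time and separate severity tiers are planned, and section 11.2.4.1 will explore models for individual outcomes. An alert that merely restates an event would show a lead time near zero.
- Predicting a later threshold crossing from earlier values of the same variable is legitimate early warning. Only use of the defining reading itself is circular.
- A prediction horizon, a minimum gap and the handling of event-time observations are ordinary SAP content, and section 11.1 defers detail to a SAP that is not shown.

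All of this stands, and it limits the point to a conditional risk. It does not remove the point: the selection of outcomes is set in the protocol, and none of the planned steps takes overlapping events out of the headline measures.

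**Conclusion.** The concern holds as a design risk, not as a demonstrated bias. The protocol permits outcome criteria and score inputs to share fields, and it separates outcomes by severity alone. Discrimination, sensitivity and the ranking of the eMOEWS against vital-signs scores can be inflated as a result.

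The size cannot be derived from the documents. On assumed values, the c-statistic rises by 0.005 to 0.10 as overlap goes from 5% to 50%, from c0 = 0.80 with c_ov of 0.90 to 1.00. With no overlap the inflation is zero. The illustration also assumes that overlapping events are scored at or close to the defining reading. The absence of a horizon or an event-time rule is not part of this finding.

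**What to change.** At the final panel mapping in section 7.2, record for each criterion whether it is defined by a vital sign or laboratory value used by any compared score, or independently of them. Keep the composite as primary. In sections 7.3.3.3 and 11.2.4.3, add a required co-reported analysis that repeats the same performance measures and all score-versus-score comparisons on independently defined events only. Leave the prediction horizon and the handling of event-time observations to the SAP.

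The cost is one extra column in the definition mapping and a repeat of analyses already planned. The restricted analysis has fewer events. Those events lean towards more severe outcomes, which section 5.1 considers too late in the course of illness, and some (transfusion, for example) may themselves be prompted by vital signs. It therefore supplements the composite and does not replace it. Tagging when the definitions are settled avoids classifying criteria after results are known.

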7.2.1 Objectives

In the three collaborator hospitals we will:

- Report the proportion of women meeting each of the new criteria and in total in WS2 retrospective datasets – comparing these proportions relative to the hospital populations with published rates for our individual criteria. Where the criteria definitions appear to under or over-capture events, we will undertake record review to inform definition adjustment where required (approximately 10 case records per event of over/under capture).
- Undertake validation of the coded criteria through examining a stratified random sample of 100 sets of records of these cases across the three sites to assess whether the codes used in the electronic data correctly identified the conditions – again if necessary, allowing criteria definition adjustment.
- Review hospital systems for recording serious events in the time period, reviewing cases identified as maternal serious incidents (maternal serious incident cohort) but not identified by our criteria to establish whether criteria definition adjustment is required.

From MBRRACE-UK we will report the proportions of women who meet the new definitions.

- Learning will be fed back to the expert panel to generate final definitions.

Further details of the statistical analyses related to workstream 1 are given in Section 11.2.1.

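### The Delphi inclusion rule joins its two thresholds with 'or', so a definition that nobody rates 7–9 can reach the final list

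*Protocol*

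**What the plan says.** Section 7.2 describes a three-round Delphi. In round 2, participants "rate definitions on a 9-point Likert scale from 1 (not important) to 9 (critically important) in round 2". After seeing the summary scores, "each member will be asked to re-score each definition using the same 9-point scale as used in Round 2". The inclusion rule for the final list comes next. A definition qualifies when it is "rated 7-9 by 70% or more of the panel or 1-3 by less than 15% in at least one stakeholder group". The protocol states the rule nowhere else.

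Two further steps come before the definitions are fixed. In section 7.2, "The final list will again be assessed by our expert panel and mapped against routine data". In section 7.2.1, after record review for over- and under-capture, coding accuracy and missed serious incidents, "Learning will be fed back to the expert panel to generate final definitions".

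The definitions matter because section 7.3.3.3 makes maternal death, near-miss and pre-near-miss, the last two as defined in WS1, "The primary outcome for MOEWS assessment for both data sources". The WS3a candidate-variable Delphi (section 7.4.1.3) reuses the procedure: "Subsequent rounds will follow the processes described in WS1".

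**The concern.** A consensus rule of this kind normally asks for two things: strong positive support and little opposition. Joined by *or*, either is enough. The second limb is a test for absence of opposition, and in one stakeholder group only. Scores of 4–6 count towards neither threshold, so lukewarm definitions pass the second limb easily. The 70% threshold decides inclusion only when every stakeholder group has at least 15% of its members scoring 1–3.

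The scope is also unclear. The first limb refers to the panel and the second to at least one stakeholder group, and the sentence does not say whether that difference is intended.

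At stake is the content of the primary composite. Weakly supported pre-near-miss definitions could become part of the outcome against which existing MOEWS are assessed and the new scores are judged. Reporting death, near-miss and pre-near-miss separately shows the components but does not change what is in the composite. In WS3a the consequence is small, because availability checks and model selection follow.

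**Working it through.** **Inputs.** From section 7.2: a 9-point scale; at least 70% of the panel scoring 7–9; under 15% scoring 1–3 in at least one stakeholder group; connective *or*. The protocol gives no panel size, number of groups or group size, and no operating figure for the rule, so there is nothing of its own to reproduce.

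**Step 1: boundary cases (no assumptions).**

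| Scores | Share 7–9 | Share 1–3 | As written | With *and* |
|---|---|---|---|---|
| Every member 4–6 | 0% | 0% in every group | included | excluded |
| One group all 4–6, all other groups all 1–3 | 0% | 0% in one group, 100% in the others | included | excluded |

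The first case is included whether the stakeholder-group phrase qualifies one limb or both, and also if the 15% limit is applied to the whole panel. The second is included only because one group is enough.

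The rule is not empty. It rejects a definition that 15% or more of every group score 1–3 and that under 70% of the panel score 7–9.

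**Step 2: how often the second limb alone admits a definition (illustration).** Assume *k* groups of *g* members rating independently, each with probability *p* of scoring 1–3. A share under 15% means at most *c* = 2 low scores when *g* = 20 (2/20 = 10%; 3/20 = 15% fails) and at most *c* = 1 when *g* = 10. Then

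P(second limb met) = 1 − [1 − F(c; g, p)]^k, with F the binomial distribution function.

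Example: *g* = 20, *p* = 0.10 gives F(2; 20, 0.10) = 0.677. With *k* = 4, 1 − 0.323⁴ = 0.989.

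| p (scoring 1–3) | g=20, k=1 | g=20, k=4 | g=10, k=1 | g=10, k=4 |
|---|---|---|---|---|
| 0.10 | 0.677 | 0.989 | 0.736 | 0.995 |
| 0.20 | 0.206 | 0.603 | 0.376 | 0.848 |
| 1/3 | 0.018 | 0.069 | 0.104 | 0.356 |
| 0.50 | 0.0002 | 0.0008 | 0.011 | 0.042 |

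The leak is largest for definitions that attract few low scores, and it closes as opposition grows.

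**Step 3: the full rule against the alternatives (illustration).** Multinomial simulation, four groups of 20, 200,000 draws:

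| Scoring 1–3 / 7–9 | As written | *And*, whole panel | *And*, both within one group |
|---|---|---|---|
| 0% / 0% | 100% | 0% | 0% |
| 10% / 50% | 98.9% | 0.02% | 19.5% |
| 20% / 30% | 60.3% | 0.0% | 0.1% |
| 5% / 75% | 100% | 87.5% | 99.6% |

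A separate run with three groups of 10 gives the same picture. With 10% scoring 1–3, 60% scoring 4–6 and 30% scoring 7–9, inclusion is 98.2% as written, against about 0.001% on the 70% threshold alone. Applying the 15% limit to the whole panel while keeping *or* still admits that definition about 82% of the time.

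**The case against.** The logic of the boundary case is not in dispute. The strongest reply concerns its consequence.

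- **The Delphi list is not the final outcome list.** The expert panel assesses it again, and record review can adjust definitions. The text does not confine that assessment to data mapping, so the panel could drop a weak definition. This stands. But no removal criterion or importance threshold is given for either step, so neither restores the 70% test once it has been bypassed.
- **Candidates are pre-selected** from WHO near-miss events, published criteria, core outcome sets, literature review and expert judgement, so a definition that everyone scores 4–6 may be rare. This is fair, and the number of definitions affected cannot be estimated. Participants can, however, add definitions in round 1.
- **The probabilities assume independent raters with the same scoring distribution in every group.** Members see summary scores before re-scoring, and stakeholder groups exist because views may differ. This also stands, so the tables are illustration only.
- **The rule cites published guidance, and section 5.2 places development of the definitions outside the current ethics application,** so a separate document might resolve the connective. That cannot be checked here, and the protocol's wording is what would be followed.
- **The effect is bounded.** Sample size (section 11.3.1) rests on severe event rates alone, and components are also analysed individually. True, but the composite remains primary.
- **An inclusive list pruned later by experts could be deliberate.** The protocol does not say so.

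**Conclusion.** The rule is wrong as written. That a definition with no score of 7–9 must be included when all scores are 4–6 follows from the sentence alone, whatever the panel size. How far the screen is weakened in practice depends on assumed group sizes, independent ratings and a common scoring distribution. Under those assumptions, definitions with about 10% low scores are nearly always included when there are several groups, however little high support they have, while definitions scored 1–3 by half the raters are almost never included. Expert review and record-based adjustment partly mitigate this but do not repair it. The point should be fixed because it is a stated numerical rule that feeds the primary composite.

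**What to change.** Replace *or* with *and*, and state the scope once for both conditions. For example: include a definition when at least 70% score it 7–9 and fewer than 15% score it 1–3, with both percentages taken either over the whole panel or within the same stakeholder group.

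The scope must be chosen explicitly, because the two versions behave differently (0.02% against 19.5% in the 10% / 50% example above). If a single group, such as patients, is meant to be able to carry a definition, keep the stakeholder-group clause and require that group to meet both conditions.

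Settle the wording before final-round scores are seen, and apply the same rule in the WS3a Delphi.

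The cost is one sentence in the protocol or Delphi analysis plan, with no extra rounds or participants. The downside is a shorter list and some loss of well-supported definitions: with 5% scoring 1–3 and 75% scoring 7–9 in four groups of 20, about 88% would still be included under the whole-panel version and 99.6% under the same-group version.
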